3.2 Analysis Populations and Subgroups

3.2.1 Definition of Analysis Populations

Safety Analysis Set

The Safety Analysis Set consists of all subjects who received at least one dose of study drug. Subjects will be analyzed according to the treatment they actually received. The Safety Analysis Set will be the analysis set used for all safety analyses.

Intent-to-Treat Set

The Intent-to-Treat set (ITT) consists of all subjects who are randomized, whether or not study drug is received. Subjects will be analyzed according to their randomized group.

Full Analysis Set (also considered the modified Intent-to-Treat set)

The Full Analysis Set (FAS) or modified Intent-to-Treat set (mITT) consists of all randomized subjects who receive at least 1 dose of study drug, and have at least 1 efficacy evaluation after receiving study drug. Subjects will be analyzed according to their randomized group. The FAS will be the primary analysis set for efficacy analyses.

Per Protocol Set

The Per Protocol Set (PP) is a subset of the FAS that includes all subjects who complete the Week 12 visit and have no major protocol deviations that are deemed to impact efficacy. These violations include but are not limited to violations of inclusion/exclusion criteria deemed to impact efficacy, inadequate study drug compliance over the dosing period as determined from the dosing information in the eCRF, usage of prohibited concomitant medications, and incorrect randomization. Subjects will be analyzed according to their randomized treatment group. The PP set will be used for the analysis of the key efficacy endpoints only.

Prior to database lock and unblinding, there will be a meeting to review protocol deviations. The threshold for percent compliance that would be considered inadequate and would result in exclusion from the per protocol set will be determined in this meeting following review of the relevant compliance information. In addition to the deviations listed above, other relevant protocol deviations, like early termination of treatment, may be identified for review.

3.2.2 Definition of Subgroups

The major sub-groups of interest are defined by age group 1: adolescent (subjects less than 18 years of age) versus adult (subjects 18 years of age and older). Additional subgroups of age (age group 2) will also be defined as follows: subjects less than 18 years of age, subjects 18 years and less than 25 years of age, and subjects 25 years and older.

3.3 Analysis Variables

3.3.1

- [REDACTED]

3.3.2

Figure 1 consists of six panels, each showing the effect of a 10% reduction in the number of individuals in a specific age group on the mean age at first marriage. The panels are arranged vertically, with the y-axis representing different age groups. The x-axis represents the mean age.

Each panel contains two bars: a solid black bar representing the original mean age and a white bar representing the mean age after the reduction. The reduction in the number of individuals leads to a decrease in the mean age at first marriage in all panels.

Panel	Original Mean Age (Black Bar)	Mean Age after Reduction (White Bar)
1	~25.5	~24.5
2	~25.5	~24.5
3	~25.5	~24.5
4	~25.5	~24.5
5	~25.5	~24.5
6	~25.5	~24.5

○

3.3.3 Safety Endpoints

- Incidence of adverse events
- Change in clinical laboratory parameters from Baseline to each post-baseline assessment
- Shift in clinical laboratory parameters from Baseline to each post-baseline assessment
- Change in vital sign measurements from Baseline to each post-baseline assessment
- Change in physical exam parameters from Baseline to each post-baseline assessment
- Change in EEG from baseline to the end of treatment
- Change in irritability from ABC-C from Baseline to each post-baseline assessment.
- Clinically important changes in seizure medication from the electronic seizure diary

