3.9.1 Adverse Events

All adverse events will be coded using the Medical Dictionary of Regulatory Activities (MedDRA) Version 19.1 and will be classified by MedDRA system organ class (SOC), high level group term (HLGT), high level term (HLT), and preferred term (PT). Analyses of adverse events will be performed using the Safety Analysis Set.

Treatment emergent adverse events (TEAEs) are any adverse events occurring or worsening in severity after the first administration of study medication. The following imputation rules will be used for missing or incomplete AE start dates:

- Missing AE start day:
 - If the partial date contains a different month from the date of first study dose, then impute it as the first day of the month.
 - If it contains the same month as the date of first dose, then impute it as date of first dose.
- Missing AE start day and month:
 - If the partial date contains a different year from the date of first dose, then impute the missing day and month as Dec 31.
 - If it contains the same year as the date of first dose, then impute the missing day and month as day and month of first dose.
- Completely missing AE date:
 - Impute the missing date as the date of first dose.

The TEAE incidence will be presented by treatment group for all subjects in the Safety Analysis Set. The number and percentage of subjects who experience at least one TEAE and the number and percentage of subjects who experience at least one TEAE within each specific SOC and PT will be presented by treatment group (placebo, combined OV101 and separate dose groups). Additionally, the incidence of TEAE within each specific SOC, HLGT, and PT and specific SOC, HLT, and PT will be presented. The 95% CIs will be displayed for the frequency of TEAEs. Treatment-related AEs will be considered those at least possibly related to investigational product based on the investigator's assessment. The number and percentage of subjects reporting serious AEs, treatment-related AEs, and AEs leading to treatment discontinuation will also be summarized for each treatment group by MedDRA SOC and PT.

The AEs of Special Interest include Dizziness, Somnolence, Nausea, Vomiting PTs, and will be reported separately.

All adverse event data including baseline adverse events will be displayed in subject data listings.

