| 
[REDACTED]
 
[REDACTED]
 
Since the targeted study population may not be compliant with certain study assessments, the highest possible level of flexibility will be applied to the schedule of assessments at each study center visit, thus minimizing the risk of missing or confounded data, while data reliability is maintained.
 |
| 
Phase of Development: Phase 2
 |
| 
Study Design: Multicenter, randomized, parallel (3-arm), double-blind, placebo-controlled
 |
| 
Study Location: Approximately 15 specialized centers across the United States of America and 1 specialized site in Israel
 |
| 
Principal Investigator: [REDACTED]
 |
| 
Study Period (first subject first visit to database lock): 1.5 year
 |
| 
Estimated date of first subject first visit: 1st Quarter 2017
 |
| 
Estimated date last subject last visit: 2nd Quarter 2018
 |
| 
Study Objectives and Endpoints:
 
The primary objective of the study is to evaluate the safety and tolerability of OV101 from Baseline to Week 6 and Week 12 in adolescent and adult subjects with AS across different dose levels and in 2 dosing schedules.
 
The following dosing schedules will be assessed against placebo:
 
Once daily (QD): An evening dose titrated to the target dose of 15 mg unless not toleratedTwice daily (BID): Evening and morning doses titrated to the target doses of 15 mg evening dose and 10 mg morning dose unless not tolerated 
The safety endpoints that relate to this objective are as follows:
 
Frequency and severity of adverse events (AEs) and serious adverse events (SAEs)Vital signs (weight, blood pressure, heart rate, and temperature)Laboratory parameters (electrolytes, lipids, glucose, hepatic, renal and pancreatic function tests, and hematology). It is in the discretion of the study center staff to apply local best practices to obtain a blood sample from the subjectIrritability will be assessed using the Aberrant Behavior Checklist – Community (ABC-C) in an attempt to assess suicidalityEEGCaregivers will maintain an electronic seizure diary. Any clinically important changes, including changes in seizure medication, will be reported as a safety eventPhysical Exam findings |

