The primary endpoint is the incidence of treatment emergent adverse events (TEAE). The Safety Analysis Set (all subjects that received at least one dose of study drug) will be used for the analysis of the TEAEs. All AEs will be coded using the latest released version of Medical Dictionary of Regulatory Activities (MedDRA) and will be classified by MedDRA system organ class (SOC), and preferred term (PT). The number and percentage of subjects who experience at least one TEAE as well as the number and percentage of subjects who experience at least one TEAE within each specific SOC and PT will be presented by treatment group.

[REDACTED]

[REDACTED]

Table S2 Schedule of Assessments

| Visit Name | [REDACTED] | [REDACTED] | Unscheduled | Phone Titrate | Phone Safety | Interim | Phone Safety | End of Treatment | Follow-up Phone* | |
|---|------------|--------------|-------------|---------------|----------------|----------------|----------------|------------------|------------------|------|
| Window | | | Any Time | +2 Days | ± 2 Days | ± 3 Days | ± 2 Days | + 3 Days | ± 2 Days | |
| Week | | D -28 to D 0 | D 1 | Any Time | D 3, 7, 10, 14 | D 31 | D 43 | D 57, 71 | D 84 | D 98 |
| ICF and Assent (Separate for Caregiver and Subject) | X | | | | | | | | | |
| Inclusion/Exclusion Criteria | X | X | | | | | | | | |
| Medical History | X | X | | | | | | | | |
| Clinical Assessment [†] | X | X | | X | X | X | X | X | X | |
| Biomarker Plasma [‡] | | X | | | | | | | X | |
| Biomarker DNA [‡] | | X | | | | | | | | |
| Molecular AS Test [§] | X | | | | | | | | | |
| Dose Titration | | | | X | X [#] | X [#] | X [#] | | | |
| Physical Exam | X | X | | | | X | | | X | |
| Vital Signs | X | X | | | | X | | | X | |
| Clinical Laboratory Tests | X | X | | | | X | | | X | |
| Serum Pregnancy Test ^{**} | X | X | | | | X | | | X | |
| EEG | | X | | | | | | | X | |
| Adverse Events | X | X | X | X | X | X | X | X | X | |
| Concomitant Medications | X | X | X | X | X | X | X | X | X | |
| Check Scales Completed by Clinician: | | | | | | | | | | |
| | [REDACTED] | | | | | | | | | |
| | [REDACTED] | | | | | | | | | |
| | [REDACTED] | | | | | | | | | |
| | [REDACTED] | | | | | | | | | |
| | [REDACTED] | | | | | | | | | |
| | [REDACTED] | | | | | | | | | |
| | [REDACTED] | | | | | | | | | |
| | [REDACTED] | | | | | | | | | |
| | [REDACTED] | | | | | | | | | |
| | [REDACTED] | | | | | | | | | |
| | [REDACTED] | | | | | | | | | |
| | [REDACTED] | | | | | | | | | |

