OV101 administration in the morning was safe at all doses [REDACTED]¹². In healthy young men, doses up to 20 mg were well tolerated when given alone as single morning doses for 5 days. In young women, a 15 mg morning dose was not well tolerated or tolerated with considerable discomfort from Day 2 and onwards. An evening dose of 15 mg was well tolerated in young women and women above 55 years for 3 consecutive days. Therefore, a 10 mg morning dose was chosen for this study. The AEs with the highest incidences were dizziness, nausea, headache, and somnolence. The majority of AEs had a rapid onset (within 1 to 2 hours post-dose) and resolved after the drug was discontinued.

Approximately 500 subjects were exposed to OV101 in clinical studies in non-insomnia-related development. The safety and tolerability profile of OV101 in the non-insomnia-related studies was similar to that in sleep disorder studies. In general, the AEs seemed to be dose related, with no AEs reported for the 5 mg dose, and only mild AEs reported for the 10 mg dose of OV101.

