9. STUDY OBJECTIVES AND ENDPOINTS

9.1 Primary Objectives

The primary objective of the study is to evaluate the safety and tolerability of OV101 from Baseline to Week 6 and Week 12 in adolescent and adult subjects with AS across different dose levels and in 2 dosing schedules.

[figure not shown]
The following dosing schedules will be assessed against placebo:

- Once daily (QD): An evening dose titrated to the target dose of 15 mg unless not tolerated
- Twice daily (BID): Evening and morning doses titrated to the target doses of 15 mg evening dose and 10 mg morning dose unless not tolerated

The safety endpoints that relate to this objective are as follows:

- Frequency and severity of AEs and serious adverse events (SAEs)
- Vital signs (weight, blood pressure, heart rate, and temperature)
- Laboratory parameters (electrolytes, lipids, glucose, renal, hepatic and pancreatic function tests, and hematology). It is in the discretion of the study center staff to apply the best local practices to obtain a blood sample from the subject. Laboratory sampling should be done towards the end of a visit to minimize any confounding impact on subject performance
- Irritability will be assessed using the Aberrant Behavior Checklist – Community (ABC-C), Irritability subscale as a surrogate measure for suicidality
- EEG
- Caregivers will maintain an electronic seizure diary. Any clinically important changes, including changes in seizure medication, will be reported as a safety event
- Physical Exam findings

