16.1.1.2 Recording of Adverse Events

For the purposes of this study, any detrimental change in the subject's condition, from the screening visit (Day -28) and up to completion of the follow-up period after the last administration of study drug (Day 98 follow-up phone visit) should be considered an AE and must be recorded on the eCRF.

All SAEs and AEs will be recorded starting from the screening visit (Day -28).

All ongoing AEs should be followed up for 30 days after the last administration of study drug, with the exception of any ongoing study drug-related AEs, which should be followed until resolution, unless in the investigator's opinion, the AE is unlikely to resolve due to the subject's underlying disease. Any new SAEs occurring up to 28 days after the last administration of study drug (Day 98 follow-up phone visit) should be reported according to Section 16.1.1.6.

At any time after the follow-up visit, if an investigator learns of an SAE that can be reasonably related to study drug, he/she should promptly notify Ovid Therapeutics Inc.

The severity of AEs and SAEs will be graded using the National Cancer Institute Common Terminology Criteria for Adverse Events (CTCAE, Version 4). Any AE not listed in the CTCAE will be graded as follows:

| Severity Grade | Definition |
|----------------|------------------------------------|
| 1 | Mild AE |
| 2 | Moderate AE |
| 3 | Severe or medically significant AE |
| 4 | Life-threatening AE |
| 5 | Death related to AE |

It is important to distinguish between serious and severe AEs. Severity is a measure of intensity whereas seriousness is defined by the criteria in Section 16.1.1.

An AE of severe intensity need not necessarily be considered serious. For example, nausea that persists for several hours may be considered severe nausea, but not an SAE. On the other hand, a stroke that results in only a limited degree of disability may be considered a mild stroke but would be an SAE.

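### Severity is part of the protocol's first-listed safety endpoint, but no planned analysis is committed to summarise it by treatment group

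*SAP*

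**What the plan says.** **Where severity is named.** Protocol section 9.1 opens its list of safety endpoints for the primary objective with "Frequency and severity of AEs and serious adverse events (SAEs". The synopsis has the same item: "Frequency and severity of adverse events (AEs) and serious adverse events (SAEs".

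**Where severity is collected.** Protocol section 16.1.1.2 states: "The severity of AEs and SAEs will be graded using the National Cancer Institute Common Terminology Criteria for Adverse Events (CTCAE, Version 4". AEs not covered by CTCAE are graded on the protocol's own 1 to 5 scale. Section 16.1.1.6 includes maximum intensity among the variables recorded for each AE.

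**Where only incidence is analysed.**
- Synopsis, statistical methods: "The primary endpoint is the incidence of treatment emergent adverse events (TEAE".
- Protocol 17.2.3.2 and 17.2.4.1: serious, treatment-related, discontinuation and special-interest events, with no summary by severity.
- SAP 3.3.3: "Incidence of adverse events".
- SAP 3.9.1: subjects with any TEAE and those with "at least one TEAE within each specific SOC and PT will be presented by treatment group", further tables by HLGT and HLT, the same categories of event as the protocol, and subject listings of all AE data. Severity appears only in the definition of a TEAE.
- SAP Section 6: Tables 14.3.1.1 to 14.3.1.8 are all visible, and no title refers to severity or grade.

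**The concern.** The trial's primary objective is safety and tolerability of two OV101 schedules against placebo. A count of subjects with at least one event treats a mild episode of nausea and a severe one alike. This matters more here because the protocol requires intolerance that slows or reverses titration to be recorded as an AE (sections 12.1.3.5, 12.1.3.6 and 16.1.1). Mild and severe intolerance therefore enter the same incidence figure.

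The sponsor also describes earlier experience partly by intensity. Protocol 8.1 says AEs in the non-insomnia studies seemed dose related, "with no AEs reported for the 5 mg dose, and only mild AEs reported for the 10 mg dose of OV101", and sections 8.1 and 10.3 describe most AEs in adults as mild to moderate. No planned by-arm table in this trial could be set beside those statements.

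**Working it through.** The main check is a comparison of texts. The arithmetic shows only what incidence alone can hide and what precision a severity summary would have.

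1. **Is severity a named endpoint component?** Yes, in protocol 9.1 and the synopsis.

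2. **Are the data collected?** Yes, under protocol 16.1.1.2 and 16.1.1.6.

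3. **Does any analysis text commit to a by-arm severity summary?**
   - Synopsis statistics, protocol 17.2.3.2 and 17.2.4.1: no.
   - SAP 3.3.3 and 3.9.1: no.
   - Tables 14.3.1.2 to 14.3.1.8: no, by title.
   - Table 14.3.1.1 (overall TEAE summary): contents not specified, so a severity row is neither promised nor excluded.

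4. **Do the other planned tables stand in for it?** Not fully. Protocol 16.1.1.2 distinguishes serious from severe and gives severe nausea as an event that need not be serious. Dose reduction is allowed, so a severe event can be followed by a lower dose without entering the discontinuation table. The treatment-related table sorts by cause.

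5. **The plan's own precision figures** (protocol 17.1). Half-width = 1.96 × √(p(1 − p)/n) with p = 0.25:
   - n = 25: 1.96 × √(0.1875/25) = 0.170, the stated 17%.
   - n = 20: 1.96 × √(0.1875/20) = 0.190, the stated 19%.

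   Both reproduce. They concern AE incidence; the documents give no precision for severe events.

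6. **Illustration with assumed counts** (not from the documents). Two arms of 25 each have 15 subjects with any TEAE: 15/25 = 60%. In one arm all events are grade 1, so 0/25 have grade 3 or higher. In the other, 5/25 = 20% do. Every SOC and PT incidence row can be identical.

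7. **What a grade 3 or higher summary would show if no such event occurred.** The exact two-sided 95% upper limit for 0 of n is 1 − 0.025^(1/n):
   - n = 25: 13.7%
   - n = 20: 16.8%
   - n = 50 (both OV101 arms combined): 7.1%

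**The case against.** Four points can be made for the plan as it stands.

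**Severity is not lost.** A reader might infer that half of the endpoint goes unreported. The documents do not support that: SAP 3.9.1 puts all AE data in subject listings and SAP 3.1 says the same of all clinical data. With about 75 subjects, those listings can be read. This point stands, and the gap is confined to summaries by arm.

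**The SAP did not remove a primary endpoint.** A reader might infer an undeclared change that SAP 3.11 should have listed. But section 9.1 names none of its seven safety endpoints as primary. The synopsis names TEAE incidence as primary, and the SAP analyses it. On severity the SAP follows protocol 17.2.4.1. This also stands: the conflict is between the protocol's endpoint list and its own statistical text. It explains the omission without resolving it, because 9.1 still names severity and the SAP is where its analysis should be specified.

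**Other outputs bear on tolerability.** Serious, treatment-related, discontinuation and special-interest tables are planned, as are reasons for discontinuation, compliance, days on treatment and capsules taken. In a real trial these might well separate the two arms of the illustration, which compares incidence rows only. They are partial substitutes and none measures intensity.

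**The background sentence is limited.** It separates 5 mg from 10 mg by whether AEs occurred, mentions intensity only for 10 mg, and gives none for 15 mg. It shows that the sponsor uses intensity as a descriptor. It does not show that earlier doses were distinguished by severity.

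**Conclusion.** The point holds as a gap between a named endpoint and the analyses committed to. Severity is in the first-listed safety endpoint and is recorded for each AE, yet no statistical text in either document commits to summarising it by treatment group. In a trial whose primary objective is tolerability, that is more than a formatting detail. It is still a reporting gap that should be closed: it does not undermine the planned incidence analysis.

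The conclusion rests on the visible text. Table 14.3.1.1 may turn out to carry severity rows, and the body of the SAP's list of listings is not visible. Confidence is therefore high that a by-arm summary is not specified, and lower that none would be produced. The 60% and 20% figures are assumed; the size of any real difference in severity between schedules cannot be derived from the documents.

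**What to change.** - **SAP 3.3.3:** define the endpoint as frequency and severity of AEs, in line with protocol 9.1.
- **SAP 3.9.1 and Section 6:** add a summary of TEAEs by maximum severity grade per subject for QD, BID, combined OV101 and placebo. Use CTCAE version 4, or the protocol's 1 to 5 scale for AEs not listed in CTCAE, and say that both feed the same table. Cover at least all TEAEs together and the four special-interest terms (dizziness, somnolence, nausea, vomiting), and preferably SOC and PT.
- **Same section:** add the number and percentage of subjects with any grade 3 or higher TEAE, with a 95% CI, and state how a missing grade is handled.
- **If the sponsor prefers listings only:** say so in SAP 3.11 with the reason.

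The cost is a few sentences and one extra table from data already collected. At about 25 subjects per arm, possibly 20, a full SOC and PT layout by grade will have many empty or single-count cells. If that is judged unhelpful, grade rows in Table 14.3.1.1 and in the special-interest table (14.3.1.8) would meet the minimum.

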3.3.4 Other Variables

- Incidence of discontinuations and reasons for discontinuations from the study
- Incidence of concomitant medications used
- Compliance, days on treatment, and total number of capsules taken

3.4 Subjects Disposition and Evaluability

3.4.1 Subject Disposition

Subject disposition (screening, randomization, study completion) will be presented overall and by treatment group. The number and percentage of subjects evaluated for each subject population will be presented overall and by treatment group. The numbers of subjects completing and not completing the study, as well as reasons for subject discontinuations will also be summarized overall and by treatment group.

